**A. SPECIFIC AIMS**

---

The aim of this study is to assess the effects of *N*-acetylcysteine (NAC) on initial cessation and relapse prevention in adult cigarette smokers. Specifically, this study has the following aims: **Aim 1)** Examine the efficacy of NAC, compared to placebo, in helping smokers achieve three days of continuous abstinence; **Aim 2)** Among those who maintain initial 3-day abstinence, examine the time to relapse over the 8-week intervention between NAC and placebo groups; **Aim 3)** Assess 7-day point prevalence abstinence at the 8-week end-of-treatment study visit in order to obtain effect sizes and estimates of variability to power a randomized clinical trial.

---

**B. BACKGROUND AND SIGNIFICANCE**

---

Cigarette smoking remains the leading cause of preventable death in the United States (US) (1), and approximately 17.8% of the general population are current cigarette smokers (2). While the continued decrease in smoking prevalence is encouraging, initiating and maintaining abstinence remains a substantial hurdle for the vast majority of those with tobacco use disorder (TUD). Fewer than one in ten smokers making an unassisted quit attempt are likely to succeed over the long-term (3-6), making relapse the most likely outcome of any given quit attempt (7). Evidence-based pharmacotherapeutic interventions for TUD have been shown to increase the odds of quitting smoking by two to threefold compared to placebo (8). However, even with the assistance of pharmacotherapy, abstinence rates are still only approximately 40-50% (9-12). This high rate of treatment failure indicates a pressing need to expand smoking cessation pharmacotherapy options to focus not only on promoting initial cessation, but also on the prevention of relapse over a sustained period of time to improve treatment outcomes.

Within the preclinical literature on addiction, glutamate has emerged as a potential pharmacotherapeutic target in the treatment of substance use disorders (SUDs) (13-17). Specific attention has been given to *N*-Acetylcysteine (NAC) for the treatment and management of SUDs due to its actions on the glutamatergic system. Preclinical models have shown that NAC appears to restore normal glutamate signaling and robustly decreases the reinstatement of heroin, cocaine, and nicotine seeking (18-25). Clinical research focused on NAC for SUDs has demonstrated evidence of reduced drug use and/or reduced craving and withdrawal scores under NAC administration among cocaine and cannabis dependent participants (26-30), in addition to tolerability and safety of therapeutic doses. Unfortunately, randomized controlled trials evaluating NAC's efficacy for SUDs have been disappointingly mixed (31-33). Concurrent with the SUD treatment studies described here, preliminary pilot studies have been conducted extending the use of NAC as a pharmacotherapy for TUD.

To this point, four pilot studies have been conducted examining NAC as a pharmacotherapy for TUD. Two studies assessed cigarette/nicotine withdrawal, craving, reward, and neural functional connectivity between NAC and placebo treated participants during brief periods of abstinence (three days) in an outpatient setting. Results from one study found that NAC reduced subjective reward of the first cigarette smoked after abstinence (34), while the

second study (conducted at MUSC; PI [name]) found that NAC treated participants were better able to achieve abstinence during the three day period, reported lower craving scores, and demonstrated stronger corticostriatal connectivity (35). Additionally, two pilot clinical trials assessed smoking abstinence during NAC or placebo administration. One study (also conducted at MUSC; PI [name]) found a trend towards fewer cigarettes per day for the NAC group, but no benefit on biochemical measures of smoking, craving or withdrawal ratings (19). However, another pilot study demonstrated impressive abstinence rates favoring NAC compared to placebo at the end of 12 weeks of treatment (47% in the NAC group versus 21% in the placebo group) (36).

Currently, NAC's efficacy has not been firmly established and explanation of the mixed results in the literature has not been articulated. One potential hypothesis has been offered to explain negative results and to inform the implementation of NAC as a pharmacotherapy. It has been suggested that the mixed results in the literature may be due to the conditions under which NAC is administered (i.e., during periods of abstinence versus active use of the drug). Studies that have focused on NAC's ability to promote initial cessation have generally demonstrated inconsistent findings. These inconsistencies suggest that NAC appears to have questionable efficacy when administered during periods of active drug use. However, a growing body of evidence suggests that NAC's efficacy may rely on medication administration under conditions of abstinence. NAC may be more efficacious in preventing relapse, and may even assist in achieving initial abstinence, but only in the presence of other abstinence-targeted elements (i.e., contingency management, other pharmacotherapies, etc.). Indeed, many of the most robust and positive findings in support of NAC from preclinical models have been in the context of a reinstatement model that mimics relapse vulnerability. Additionally, LaRowe and colleagues (32) found that participants who were abstinent from cocaine at least one week prior to study entry had better outcomes (i.e., longer time to relapse and reduced craving) in the higher dose NAC condition compared to placebo, though no overall effect of NAC was found in this study. Finally, much of the early clinical work demonstrating reduced craving, withdrawal, and drug reward with NAC was conducted through inpatient study designs, where active drug use was prohibited or was experimentally administered (27, 28, 30).

Based on the previous work conducted with NAC, two key gaps in the literature have emerged. First, additional data are needed to understand if NAC is effective in initiating abstinence. Second, is NAC effective as a relapse prevention aid, following a period of abstinence, or does it assist with both? NAC administration during abstinence may be a key feature contributing to positive results, and may also help to explain the negative results. Though this hypothesis has support, it has yet to be directly tested. These questions represent the next steps in the exploration of NAC as a pharmacotherapy for TUD, prior to large-scale evaluation and implementation of NAC among clinical populations. Therefore, this study will focus specifically on NAC as a pharmacotherapy for TUD and will evaluate NAC's influence on initial cessation and relapse prevention over 8 weeks in adult smokers.

### **C. PRELIMINARY STUDIES**

---

As part of an ongoing collaboration with preclinical and neuroimaging colleagues, [name] has contributed to translational efforts to better understand NAC's neurobiological mechanisms of action. As part of this collaboration, [name] was involved in a pilot study that administered NAC, while also reinforcing abstinence from smoking for three days (35). In addition to promising smoking outcomes from this study, it also provided demonstration of feasibility for aspects of this proposed application, including: the ability to successfully reinforce three days of abstinence from smoking and procedural details in reinforcing abstinence (i.e., adequate compensation for abstinence). Within that study, the majority of participants given NAC achieved high rates of abstinence on the second and third days of reinforced abstinence (75% and 100%, respectively). Conversely, those randomized to the placebo condition achieved lower rates of abstinence on the second and third days (12.5% and 25%, respectively). Additionally, [name] has experience in the conduct of a human laboratory study that reinforced a brief period of abstinence (18 hours) following one week of varenicline titration (37).

[name] and the research team on this study have experience in safely administering NAC to adult and adolescent study participants. Specifically, the Co-Investigator and medical clinician on this study, [name] has extensive experience in conducting medication trials with NAC (FDA IND approval # 78927) and will provide medical oversight and adverse event review for the following protocol. A number of studies have been published by the research team and collaborators to demonstrate adequate safety and tolerability of study medication (19, 26, 32, 33, 35, 38). These studies have largely shown that NAC is well tolerated and no differences were found in the occurrence of adverse events between treatment groups. The PI and research team are prepared to administer NAC or placebo to adult smokers and address all adverse events that may emerge as part of this study protocol. In summary, [name] and research team have ample experience conducting trials with NAC in substance dependent adults and adolescents, with careful attention to safety and tolerability.

## **D. RESEARCH DESIGN AND METHODS (including data analysis)**

### Study Design

This study will assess NAC as both an initial cessation aid and relapse prevention aid. Interested individuals will receive a brief telephone screening to determine if they may be eligible to participate. They will then be scheduled for an initial assessment, consisting of informed consent, followed by completion of self-report questionnaires and semi-structured interviews to determine eligibility. If participants are eligible for the study, they will be asked to return for their training visit. At the training visit, participants will be given instructions on completing remote surveys and counseling in preparation for their target quit date (TQD). Participants will then return for their randomization visit (Day 0), which will occur within 30 days of screening. On Day 0, participants will be randomized to receive double-blind NAC or placebo for eight weeks. Urn randomization procedures will be used.

Participants will then be contingently reinforced for abstinence from smoking for three days while taking study medication. Following three days of reinforced abstinence, participants will complete the remaining 8-week treatment intervention. Medication will be terminated at the Week 8 end-of treatment (EOT) visit.

Participants will then return at Week 12 (Day 84) for 4-week post-treatment follow-up visit to assess smoking status. The study design is shown in Figure 1. If

participants have unexpected conflicts after randomization and cannot keep weekly visit schedule (i.e. transportation issues or visit activity during an extended holiday), then participants may be eligible to complete weekly visits remotely via telephone call. During remote visits, Participants will be called via phone and all protocol procedures will be completed with the exception of a CO sample. Biologic collection (i.e. urine sample) may be obtained with proper planning, the participant may be given the opportunity and supplies required to complete an offsite/at home urine collection should they be willing to follow the proper collection and storage of a sample. Participants will be assessed for AE's, medication compliance, and will complete emailed surveys all within the assigned visit window. A CO sample will be collected at the participants next in-clinic visit. This option will only be used as a last resort for uninterrupted study participation.

[figure not shown]

Figure 1. Study design

### Assessment

Formal written consent will be obtained from all new participants enrolled in this project. Following the policies of the MUSC Institutional Review Board, written informed consent will be obtained and documented by approved research staff before any study-related procedures are performed. Informed consent will be obtained in a private research office. Each individual may take as much time as they like to decide if they do or do not wish to participate. Following informed consent, participants will complete self-report questionnaires, semi-structured interviews, a medical history, and will also be asked to provide breath and urine samples to assess smoking status, pregnancy status, and to screen for illicit drug use. [name] (PI) will review all screening material and, in consultation with [name] (Co-I and medical clinician) and/or other approved medical clinicians on this protocol, will determine study eligibility for each participant. Additionally, during the assessment visit, participants will be asked to sign a "lifestyle agreement" in which they agree to important aspects of the study procedures (e.g., abstaining from tobacco products and smoking cessation products, engaging in the 3-day quit attempt, and using some form of birth control [female participants only]). This agreement will help to promote adherence to study procedures and provide an additional opportunity to stress the importance of these protocol components. If participants remain interested in the study and meet eligibility criteria, they will be asked to complete morning report surveys through REDCap during the study. The morning report will ask about how many cigarettes were smoked the day prior, if alcohol and/or drugs were consumed, and time of medication dosing (added to survey after Randomization/Day0). Participants will be asked to begin completing morning reports following their screening visit. Links to access the morning report will be sent to participants through their mobile phone and their email address. Participants may complete morning reports on either their smartphone or on a computer.

### Training Visit

Participants will return to the clinic to be trained on using a breath carbon monoxide (CO) monitor and prepared for the TQD. Participants will be provided with a breath CO monitor, so that they may take CO readings at home or in a private location of their choosing. Breath CO samples will be taken remotely and videos will be submitted

via REDCap surveys to confirm that the participant is trained and/or prepared for Randomization. Participants may use their personal mobile phones for video submission. If they do not have a smartphone, one will be loaned to them at the training visit. Video submissions may only be completed on a smartphone (cannot be completed on a computer). A survey link will be sent to the participant via text message. Video capture will occur as part of the REDCap survey. Videos are automatically stored on Android smartphones, and participants will be informed of that so they can delete the files, if necessary. Participants using iPhones (and using loaner iPhones from our group) will not have stored videos on their phone and nothing will need to be deleted. At Training, participants will be asked to sign an "equipment honor statement" in which they agree to: 1) return all equipment loaned (as applicable) back to the study team, 2) acknowledge that if equipment is not returned or returned in poor condition it will affect their equipment bonus compensation, and 3) agree to refrain from completing mobile surveys when unsafe to do so (i.e. while driving). This agreement will reinforce importance of returning loaned equipment to study team and promote safe usage of equipment by participants.

#### Randomization (Day 0)/Abstinence Period

Participants will return to the clinic on Day 0 to receive study medication. Participants will begin taking study medication on Day 1. Day 1 will also be when they abstain from smoking. Participants will be instructed to stop smoking no later than 11:59 pm on the night of their Day 0 visit. Participants will be reinforced contingently for abstinence from smoking on Days 1-3. Two breath CO samples per day will be taken remotely and videos will be submitted via REDCap surveys to confirm smoking status during that time (during Days 1-6 of the study). In order to monitor and confirm medication adherence during the first six days of the study, participants will also record themselves taking their morning and evening medication doses. These videos will be submitted via REDCap surveys at the same time as the CO samples are submitted. If the participant prefers to take the medication before the first prompt of the morning, they will be able to record their medication video and upload the file when completing the survey. Abstinence from smoking is defined as a breath CO of  $\leq$  6 parts per million (ppm) and/or a 50-75% reduction from the participant's average screening and Day 0 breath CO samples. Participants will continue to complete the morning reports through REDCap through the remainder of the study.

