#### Statistical Analyses

Categorical clinical and demographic variables will be assessed by chi-square tests of independence, while continuous variables will be assessed using Student's *t*-test. In addition to baseline group differences, preliminary analysis of baseline characteristics with tobacco use outcomes of interest will examine significant correlates of abstinence in the study population. Characteristics found to be significantly associated with tobacco abstinence and relapse outcomes will be included as covariates in the initial stages of model development. The primary measure of interest will be the proportion of biochemically confirmed and self-reported 3-day abstinence (defined as twice per day breath CO measures of  $\leq 6$  ppm or a 75% reduction from the participant's averaged baseline and Day 0 CO samples). The proportion of participants achieving 3-day abstinence will be compared between NAC and placebo treatment groups using logistic regression models (Specific Aim #1). Secondarily, there is great interest in determining if those who achieved 3-day abstinence under NAC treatment were less likely to relapse over the course of eight weeks compared than those who achieved abstinence under placebo treatment (Specific Aim #2). Daily smoking diary data will be used in conjunction with weekly breath CO measures to determine if and when relapse to regular smoking returned during the eight weeks of treatment with the study drug. Based on recommendations for defining treatment failure, relapse will be defined as smoking during seven consecutive days or smoking at least once over two consecutive weeks (54). This definition will account for regular and irregular smoking over the course of the eight-week intervention phase. Cox proportional hazards models will be developed to assess the efficacy of NAC in prolonging abstinence and preventing relapse. Additionally, end of study 7-day point prevalence abstinence will be assessed through the proportion of self-reported and biochemically confirmed 7-day abstinence. Biochemical confirmation for end-of-study abstinence is defined as a negative daily breath CO measures ( $\leq 6$  ppm or 75% reduction from baseline) and a negative urine cotinine measure ( $<80$  ng/mL). The main effect of NAC versus placebo on the proportion of abstinent participants will be assessed using logistic regression models. All stated models will be computed both unadjusted and adjusted for significant covariates and confounders found in the preliminary analysis. All randomized participants will be included in the primary analysis (intent-to-treat; ITT) and participants will be deemed not-abstinent at any missed visit or missing CO measure (drop-out/loss-to-follow up included). In addition to the primary ITT analyses,

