
additional exploratory approaches (e.g., modified ITT models, per protocol analysis, and completer analysis) will be undertaken as indicated and a sensitivity analysis comparing these models to the ITT model will be completed.

**Power and Sample Size.** This study is largely focused on obtaining preliminary data to inform and power a larger randomized controlled trial to assess NAC for TUD. However, the proposed sample size (N=110) of this study will allow for adequate power to detect differences between treatment groups for the first two stated aims and hypotheses. This study is powered to assess the hypothesis that NAC, as compared to placebo, will promote greater abstinence from smoking during a 3-day quit attempt at the beginning of an eight week randomized controlled trial. In a pilot trial (N=16) investigating NAC as a cessation aid over three days of reinforced abstinence, [name] and colleagues (35) found that the majority of study participants given NAC achieved high rates of abstinence on the second and third days of reinforced abstinence (75% and 100%, respectively) following a target quit date. Conversely, those randomized to the placebo condition achieved lower rates of abstinence on the second and third days (12.5% and 25%, respectively). With a proposed sample size in the current study of 110 participants (55 randomized to each treatment assignment), this number will provide sufficient power (80%) with a type 1 error rate of 5% to detect abstinence rate differences of as low as 20% between those randomized to NAC versus placebo.

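### The primary 3-day outcome counts a Day 1 morning CO reading that can still reflect smoking the protocol allowed on Day 0, so some compliant quitters may be scored as failures

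*Combined protocol and SAP*

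**What the plan says.** Timing comes from the Randomization (Day 0)/Abstinence Period section. On the last permitted smoking: "Participants will be instructed to stop smoking no later than 11:59 pm on the night of their Day 0 visit". On the drug: "Participants will begin taking study medication on Day 1". On sampling, which runs over Days 1-6: "Two breath CO samples per day will be taken remotely and videos will be submitted". Participants also film their morning and evening doses: "These videos will be submitted via REDCap surveys at the same time as the CO samples are submitted". The section refers to a first morning prompt but gives no clock time, and it sets no minimum interval since the last cigarette.

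The primary outcome is in Statistical Analyses. Three-day abstinence needs self-report plus biochemical confirmation, "defined as twice per day breath CO measures of" 6 ppm or less, or "a 75% reduction from the participant's averaged baseline and Day 0 CO samples". The same paragraph treats a missing CO measure as not abstinent. No reading is exempted.

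The Abstinence Period section words the relative criterion differently: a "50-75% reduction from the participant's average screening and Day 0 breath CO samples", joined to the 6 ppm limit by and/or.

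The Baseline Screening Assessments list (item 12) describes breath CO as a measure of what remains from recent smoking.

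**The concern.** Read together, these passages make six readings count over Days 1-3. The first is taken in the morning of Day 1, close to the first dose, after smoking was allowed until just before midnight. That reading cannot cleanly separate permitted smoking before midnight from smoking soon after it, and almost no drug exposure precedes it.

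Aim 1 asks whether NAC helps smokers reach three days of continuous abstinence. A participant who follows the stopping instruction exactly could be scored a failure for CO left over from Day 0. If that happens at a similar rate in both arms, the observed difference shrinks. The same people also drop out of the abstainer set used for Aim 2.

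**Working it through.** **The plan's own power figure.** The Power and Sample Size paragraph states 80% power for a 20-point difference with 55 per arm and 5% type 1 error, without a placebo rate or sidedness. I used power = Φ[(Δ − z·SE0)/SE1], where SE0 = √(2p̄(1−p̄)/55), SE1 = √([p1(1−p1)+p2(1−p2)]/55) and z = 1.96.

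- Two-sided, 80% for 20 points is reached only if the placebo rate is about 7% or lower, or 73% or higher (7% vs 27%: 80.6%).
- One-sided at 12.5% vs 32.5%, power is 81.4%.
- At the plan's low scenario, 30% vs 50%: SE0 = 0.0934, SE1 = 0.0915, (0.20 − 0.1831)/0.0915 = 0.185, power 57.3%.

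The stated figure therefore cannot be reproduced uniquely. That is a separate matter; 57.3% serves below only as a starting point.

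**Residual CO.** Assumptions not in the documents: first-order decay, half-life h of 2-8 h, and t = 6-10 h from the last cigarette to the reading. I also take CO at the last cigarette to equal the participant's baseline/Day 0 average.

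Residual fraction = 0.5^(t/h). A compliant quitter fails only if the fraction exceeds 25% (75% rule missed) and fraction × evening CO exceeds 6 ppm. Meeting the 75% rule takes two half-lives. At t = 8 h:

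| Half-life | Residual | 75% rule | Evening CO above which a compliant quitter fails |
|---|---|---|---|
| 2 h | 6% | met | none fail |
| 3 h | 16% | met | none fail |
| 4 h | 25% | just met | none fail |
| 5 h | 33% | missed | 6/0.330 = 18.2 ppm |
| 6 h | 40% | missed | 6/0.397 = 15.1 ppm |
| 8 h | 50% | missed | 6/0.500 = 12.0 ppm |

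Sensitivity to the assumptions:

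- At 7 h with a 4 h half-life the residual is 29.7%, and failure starts at about 20 ppm.
- With a half-life of 3 h or less and at least 6 h elapsed, nobody fails.
- Stopping at 10 pm with an 8 am reading (t = 10 h) and a 5 h half-life leaves 25%, which passes.
- Under a 50% reduction rule, failure remains only at an 8 h half-life with 6-7 h elapsed (residual 59.5% and 54.5%).
- By an evening reading at an assumed 18 h, the residual is 12.5% at a 6 h half-life and 21% at 8 h, so the 75% rule is met.

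**Effect on Aim 1, illustration only.** Let f be the share of true quitters who fail only the Day 1 morning reading. It cannot be derived from the documents. Both arms' rates are multiplied by (1 − f); 55 per arm, two-sided 5%:

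| f | 30% vs 50% becomes | Difference | Power | Power if 50% vs 75% |
|---|---|---|---|---|
| 0% | 30% vs 50% | 20 points | 57.3% | 78.1% |
| 10% | 27% vs 45% | 18 points | 50.3% | 66.6% |
| 20% | 24% vs 40% | 16 points | 43.5% | 55.6% |
| 30% | 21% vs 35% | 14 points | 37.1% | 45.5% |

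**Effect on Aim 2.** The low scenario implies 55 × (0.30 + 0.50) = 44 abstainers. At f = 20% this becomes 44 × 0.8 = 35.2.

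**The case against.** The strongest reply is that nothing here fixes the size. The half-life, the prompt time and participants' CO levels are absent from the documents, and 11:59 pm is a ceiling, so many may stop earlier. Entry requires only about five cigarettes a day, so few participants might be above the ppm limits. The planning rates of 30% and 50% may already be rates on the measured endpoint, in which case multiplying by (1 − f) counts the loss twice. All of this stands: f could be near zero, and the power table shows sensitivity, not a forecast.

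The reply also says that the problem depends on the unresolved reduction rule. That stands in part. At the 50% end of the Abstinence Period wording it mostly disappears, but the primary definition in Statistical Analyses uses 75%, and there it remains.

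Three stronger readings are tempting, and the documents do not support them:

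- A reader might infer that compliant quitters lose the Day 1 abstinence payment. The definition beside the reinforcement procedure accepts 6 ppm and/or a 50-75% reduction. If the 50% end applies as an alternative, the residuals of 25-40% shown at 8 h for half-lives of 4-6 h would pass, so a lost payment cannot be asserted.
- A reader might infer bias towards one arm. The reading comes around the first dose in both arms, so similar misclassification is the reasonable expectation.
- A reader might take the pilot summary, "high rates of abstinence on the second and third days of reinforced abstinence (75% and 100%, respectively) following a target quit date", as evidence that Day 1 readings were known to be unreliable. It shows only that no Day 1 rate is cited, not how Day 1 was handled.

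Finally, dropping the first reading weakens verification of early Day 1 abstinence, in a trial that describes a 72-hour abstinence period. That cost is real, but it is small if both versions are reported.

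**Conclusion.** The point holds as a scoring weakness of unknown size. On the text, the Day 1 morning reading counts towards the primary outcome, falls around the first dose and follows smoking permitted until just before midnight. Under the 75% rule a compliant quitter can therefore be misclassified.

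Whether this happens often rests on assumptions outside the documents. With evening CO equal to baseline and 8 h elapsed, it requires a half-life longer than 4 h and evening CO above about 18 ppm at 5 h or 15 ppm at 6 h. Earlier stopping, faster elimination or a 50% rule removes most or all of it. Where it occurs, the expected effect is dilution of the Aim 1 difference and a smaller Aim 2 subset, not a spurious benefit.

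**What to change.** 1. Reconcile the 50-75% reduction wording in the Abstinence Period section with the 75% rule in Statistical Analyses, so that one definition of abstinence applies.
2. Before unblinding, define the primary 3-day outcome from the Day 1 evening reading onward: five CO readings plus self-reported abstinence on Days 1-3.
3. Keep collecting the Day 1 morning reading, and report the six-reading version as a prespecified sensitivity analysis. The gap between the two versions, by arm, will show how much the first reading mattered.

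The cost is a wording change in two sections, with no new procedure or data. The downside is that smoking early on Day 1 would rest on self-report and the evening reading.
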